Note: if the clinical attending physician believes that bacterial pneumonia is likely and requires a second antibacterial agent for "atypical" infection (an uncommon occurrence in COVID-19), patients may receive another agent (e.g., doxycycline or levofloxacin) as appropriate at the clinician's discretion.

5.2.2. Azithromycin. Patients in the azithromycin arm will receive azithromycin 500mg on day 1 plus 250mg daily on days 2-5 (may be administered IV per clinician preference).

5.3 Study Assessments. Coordinators and/or data queries will classify the COVID Ordinal Outcomes Scale on days 1–7, 14. They will also review for adverse events, including especially rash, self-report of visual changes, or symptomatic hypoglycemia. They will ensure that an EKG is performed at 24 to 48 hours post-randomization time. If a clinical EKG is not performed during this timeframe, a research EKG will be performed. In addition, ventilator status and ICU and hospital stay (using the last-off method) will be used to determine ventilator- and ICU-free days at 28 days using the worst rank ordinal technique, whereby death is scored as -1 days. In addition, coordinators and/or data queries will classify the COVID Ordinal Outcomes Scale on day 14. If this cannot be determined from the medical record, the patient will be contacted via telephone, mail, or electronic methods to determine their status on day 14.

5.2.4 Six-month assessment. A brief visit will ascertain the EQ-5D-5L to measure quality of life. Mortality and readmissions will also be assessed at that visit, which may be performed by telephone, electronic means, or in-person, depending on the subject's needs and preferences.

5.4 Approach to potential risks. Hydroxychloroquine has been used in many thousands of patients as an anti-malarial agent and in systemic lupus erythematosus and rheumatoid arthritis as a mild anti-inflammatory agent. The safety has been well established. Azithromycin has been used in millions of patients and is effective against the causes of bacterial pneumonia. Its immunomodulatory effects are also of interest in a variety of syndromes. While both agents have known side effects, such side effects are generally rare and well-tolerated.

This pragmatic study protocol is designed to optimally protect patients against risk through careful choice of exclusion criteria, pragmatic monitoring for common adverse events, and careful oversight by a DSMB.

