5.4.1 Potential risks and risk mitigation. The package insert for hydroxychloroquine lists visual impairment, cardiac impairment, QTc prolongation, worsening of psoriasis or porphyria, proximal myoneuropathy, suicidality, and hypoglycemia. Other reported risks include nausea, diarrhea, vomiting, abdominal pain, headache, dizziness, allergic reactions, rash, low blood counts, seizures, and death. All of these risks are quite rare and where observed are seen after prolonged administration, generally in the range of years. While ocular examinations are recommended after a year (and for acute symptoms), routine ocular examinations have never been recommended for brief duration of therapy. While QTc prolongation has been described, it is generally modest, and routine EKG monitoring is not normally practiced with administration of hydroxychloroquine. In addition, there is some concern that in patients with very low body weight or with low GFR the risk of adverse events may be increased. The potential risks of azithromycin primarily relate to QTc prolongation and *Clostridioides difficile* infection (CDI). Both are clearly described but quite rare with azithromycin.¹⁹ Additional risks include nausea, diarrhea, vomiting, and abdominal pain, allergic reactions, rash, infusion site reaction when given through a vein, abnormal liver function, drug interactions, development of drug-resistant bacteria, heart problems, muscle weakness, cardiac arrest, death. When hydroxychloroquine and azithromycin are co-administered, a modest prolongation in QTc may be observed, which is why we chose the more conservative threshold of 500msec rather than 550msec as an exclusion criterion.

In order to mitigate these risks, we have defined eligibility criteria that exclude patients with elevated risk, keep dosage low, and restrict treatment to just 5 days and avoid outpatient therapy. Patients are monitored within the hospital during treatment. Research coordinators and/or data queries will monitor for adverse events.

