After randomization, adverse events related to protocol procedures or occurring after the patient receives the first dose of study drug must be evaluated by the study investigator. If the adverse event is judged to be reportable, the investigator will report to the DSMB his/her assessment of the potential relatedness of each adverse event to study drug or study procedure. Investigators will assess whether there is a reasonable possibility that the study drug or procedure caused the event, based on the criteria outlined in Appendix 4. Investigators will also consider whether the event is unanticipated or unexplained given the patient's clinical course, previous medical conditions, and concomitant therapies.

Adverse events that will be collected prospectively as part of the study-specific outcome (and thus would not be separately reported as adverse events) are listed in Appendix 4. Study-specific outcomes will be reported as adverse events if they are both serious and Definitely or Possibly Related to study drug.

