Investigators will grade the strength of the relationship of an adverse event to esmolol or study procedures as follows:

- Definitely Related: The event follows: (a) a reasonable, temporal sequence from study drug or a study procedure; and (b) cannot be explained by the known characteristics of the patient’s clinical state or other therapies; and (c) evaluation of the patient’s clinical state indicates to the investigator that the experience is definitely related to study procedures.
- Probably or Possibly Related: The event should be assessed following the same criteria for “Definitely Related”. If in the investigator’s opinion at least one or more of the criteria are not present, then “probably” or “possibly” associated should be selected.
- Probably Not Related: The event occurred while the patient was receiving esmolol or undergoing study procedures but can reasonably be explained by the known characteristics of the patient’s clinical state or other therapies.
- Definitely Not Related: The event is definitely produced by the patient’s clinical state or by other therapies administered to the patient.
- Uncertain Relationship: The event does not meet any of the criteria previously outlined.

[figure not shown]
A4.3. CLINICAL OUTCOMES THAT MAY BE EXEMPT FROM ADVERSE EVENT REPORTING

Study-specific clinical outcomes of COVID-19 or ARDS are exempt from adverse event reporting unless the investigator deems the event to be related to the administration of study drug or the conduct of study

procedures (or of uncertain relationship). The following are examples of events that will be considered study-specific clinical outcomes

- Death (unless Definitely or Probably related to study drug or procedures)
- Respiratory events: Changes in degree of hypoxemia or its treatment
- Cardiovascular events: changes in doses of vasoactive drugs; cardiac arrest; cardiac arrhythmias.
- Organ dysfunction events: changes in the SOFA score or its constituents.
- ICU admission
- Rash
- Hypoglycemia
- Seizure
- Elevations in ALT, AST, lipase, and amylase
- Acute Kidney injury and dialysis
- Cytopenias
- Nausea/vomiting
- Impaired vision
- *C. difficile* infection

A4.4. DECISION TREE FOR REPORTING ADVERSE EVENTS

Adapted from Ranieri VM, Thompson BT, Barie PS et al. Drotrecogin alfa (activated) in adults with septic shock. *N Engl J Med.* 2012 May 31;366 (22):2055-64. Epub 2012 May 22. PubMed PMID: 22616830 with permission of [name].

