discharge. This approach will be used because persisting limitations are unlikely to have resolved and then recurred by 14 days. Similar single imputation rules will be devised for sensitivity analyses of secondary efficacy endpoints consistent with prior practice in the field and will be determined before the given analysis is performed to avoid bias from knowledge of outcomes.

Safety reporting

The HAHPs trial uses the adverse event reporting developed for the PROWESS-SHOCK trial.^{7,8} This approach is based on the high incidence of conditions resulting from the underlying disease that would be classified as adverse events if they occurred in healthy outpatients but are unlikely to be related to the study drug. Instead of being classified as adverse events, such events are monitored as study clinical or safety outcomes (Table 2). The exception to this rule are events which are either serious and study-related or which lead to permanent discontinuation of study drug. Those latter are reported as adverse events and are classified within the MedDRA taxonomy.

For reporting purposes, for each safety outcome or adverse event each patient will be classified as having experienced the outcome at least once (vs. never having experienced the outcome). We will separately provide counts (proportions) of safety outcomes and individual adverse events. In early interim analyses, comparisons of safety outcomes between treatment groups will be viewed as primarily descriptive. However, we will provide nominal p-values to compare adverse events and safety outcomes between groups without multiple comparison adjustment using the Chi square or Fisher exact test as appropriate to provide a crude assessment of the compatibility of observed differences between treatment groups with chance. Isolated p-values which are < 0.05 will be interpreted recognizing that 5% of such p-values will reach this threshold by chance in the absence of an actual effect of the treatment.

QTc was monitored at 24–48h after randomization as a study procedure. QTc monitoring at baseline was not mandatory but was described where it was available. We also described the change between baseline and 24–48h after randomization in QTc. These results will be summarized HAHPs SAP

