descriptively by treatment group. If the baseline QTc is available in at least 80% of participants, an analysis of covariance will be performed to compare follow-up QTc between treatment groups with adjustment for baseline QTc. Otherwise, a 2-sample t-test will be used to compare the follow-up QTc levels.

Table 2 Safety outcomes (measured daily for first five days)
Death unrelated to study drug or procedures
Seizure
Receipt of vasopressors
Atrial or ventricular arrhythmia
Cardiomyopathy
cardiac arrest
Hypoxemia requiring supplemental oxygen
ARDS
Mechanical ventilation
ECMO
Elevated LFTs
Pancreatitis
Acute kidney injury
Renal replacement therapy
Symptomatic hypoglycemia
Hematologic or coagulation events
Cytopenias
Severe dermatologic reaction

Nausea/vomiting
Visual changes
C. diff infection

Concomitant medications

The classes of concomitant medications listed in Table 3 were measured at baseline (before randomization) and through day 5 after randomization. Concomitant medications will be descriptively summarized overall and by treatment group. In addition, some patients in the hydroxychloroquine arm received azithromycin either before or in some cases after randomization. The proportion receiving azithromycin was recorded, and in exploratory summaries, safety outcomes will be displayed in that group as well as in the groups who received only azithromycin or only hydroxychloroquine.

Table 3. Concomitant medications
ACE inhibitors
ARBs
NSAIDs
Glucocorticoids
Immune-suppression
Chloroquine
Hydroxychloroquine
Azithromycin
Zinc
Vitamin C

Interim Monitoring.

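### Rash of any grade is exempt from adverse-event reporting, but SAP Table 2 counts only severe skin reactions, so some non-severe rash goes uncounted

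*SAP*

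**What the plan says.** Protocol 5.3 sets the review task for coordinators: "They will also review for adverse events, including especially rash, self-report of visual changes, or symptomatic hypoglycemia". Protocol 5.4.1 names rash as a possible effect of hydroxychloroquine ("Other reported risks include nausea, diarrhea, vomiting, abdominal pain, headache, dizziness, allergic reactions, rash, low blood counts, seizures, and death") and, later in the same section, of azithromycin.

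Protocol 7.1 explains why some events are not reported as adverse events. It refers to Appendix 4 for the "Adverse events that will be collected prospectively as part of the study-specific outcome (and thus would not be separately reported as adverse events". Rash is on the Appendix A4.3 list without any grade.

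The SAP (Safety reporting) describes the same exchange: "Instead of being classified as adverse events, such events are monitored as study clinical or safety outcomes (Table 2". The only skin entry in Table 2 is "Severe dermatologic reaction".

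The rules that bring an exempt event back into adverse-event reporting differ from place to place:

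- **Appendix A4.3:** listed outcomes "are exempt from adverse event reporting unless the investigator deems the event to be related" to study drug or to study "procedures (or of uncertain relationship".
- **Protocol 7.1, list of collected events:** nonserious events that are related or of uncertain relationship, and any event that permanently stops study drug.
- **Protocol 7.1, closing sentence:** "Study-specific outcomes will be reported as adverse events if they are both serious and Definitely or Possibly Related to study drug".
- **SAP, Safety reporting:** events that are serious and study-related, or that permanently stop study drug.

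**The concern.** The exemption is acceptable only if each exempt event is counted somewhere else. For rash the two lists do not match: the protocol removes all grades from adverse-event reporting, and the SAP puts back only the severe ones.

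This looks like an oversight. Of the three events that 5.3 singles out, visual changes and symptomatic hypoglycemia each have a Table 2 row in the same terms; rash does not. The skin row is the only one in Table 2 restricted by the word severe. Nausea/vomiting and cytopenias, for example, carry no such limit. Neither document explains the difference. The SAP's stated reason for the exemption is that these conditions come from the underlying disease and are unlikely to be caused by study drug. That reason fits rash poorly, since 5.4.1 lists it as a risk of both drugs.

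Safety is part of the objective in Protocol 2.2, and the SAP will give nominal p-values comparing arms on safety outcomes and adverse events. A between-arm comparison of rash is only as good as the count behind it.

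**Working it through.** No figure is at issue, so the check is to follow each kind of rash through the rules quoted above. The SAP plans two safety summaries: safety outcomes (Table 2, covering the first five days) and individual adverse events.

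| Kind of rash | Table 2 | Adverse-event summary |
|---|---|---|
| (a) Severe | Yes | Not needed for it to be counted |
| (b) Serious and related | Only if severe | Yes, under every rule |
| (c) Non-severe, permanently stops study drug | No | Yes, under the SAP exception and the 7.1 list |
| (d) Non-severe, nonserious, judged related or uncertain, drug continued | No | Yes under A4.3 and the 7.1 list; no under the 7.1 closing sentence and the SAP exception |
| (e) Non-severe, nonserious, judged unrelated, drug continued | No | No, under any rule |

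Rows (a) to (c) are counted. Row (e) is lost on every reading. Row (d) depends on which of two conflicting pairs of rules governs. The SAP is the document that defines the tables, and under its own exception row (d) is lost.

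If the wider rule (A4.3 and the 7.1 list) governs instead, row (d) is kept and row (e) is not. The only difference between them is the relatedness judgement. Protocol 5.2 makes the trial open-label, so that judgement can be made knowing which drug the patient received. If investigators attribute rash to one drug more readily than to the other, the counts would differ by arm even with equal true rates. The SAP Background says that assessors and investigators are blinded to outcomes by treatment group. That concerns results by arm. It does not say that the person judging relatedness is unaware of the patient's own allocation.

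**The case against.** **The exemption is conditional.** A4.3 lifts it for related or uncertain events, the 7.1 list collects nonserious events of that kind, and both the 7.1 list and the SAP keep any event that permanently stops study drug. This stands, and it limits the concern to rows (d) and (e). A reader might infer that ordinary rash never reaches a safety table, or that the reported rate would be near zero in both arms whatever happened. The documents do not support either inference.

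**The SAP does not cite A4.3.** It could be read as moving only the Table 2 events out of adverse-event reporting, so that non-severe rash stays under the ordinary 7.1 rule. That reading is possible. It would rescue row (d) only if the 7.1 list prevails over the closing sentence of the same section, and it would not rescue row (e).

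**Unrelated nonserious events are left out by design.** This is correct: 7.1 does not collect them for any event type unless study drug is stopped, so deleting rash from A4.3 would not bring row (e) back. But Table 2 counts other exempt items, such as nausea/vomiting and visual changes, without a severity limit or a condition on attribution. Rash is the one event singled out in 5.3 that lacks this.

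**The importance of rash can be overstated.** Its place in 5.3 is word order in an unranked list. Section 5.4.1 puts it among other reported risks of hydroxychloroquine, after the package-insert list, and calls all these risks quite rare. The case therefore rests on the instruction in 5.3 and the risk lists in 5.4.1, not on the promise in 5.7 of special attention to package-insert events.

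**Lipase and amylase.** A4.3 exempts elevations of these enzymes, and Table 2 has only pancreatitis. A reader might infer the same defect. The visit schedule in Appendix 1 has no such test, and counting pancreatitis is a reasonable choice, so the point is not pursued.

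**Conclusion.** The concern holds in limited form. Non-severe, nonserious rash judged unrelated, with study drug continued, reaches neither safety summary. The same rash judged related or of uncertain relationship is lost under the SAP exception and the closing sentence of 7.1, contrary to A4.3 and the 7.1 list. Rash that is severe, serious and related, or the cause of permanent discontinuation is counted.

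The by-arm counts would therefore be incomplete. The size cannot be stated, because the documents give no rash rate and no split by severity or attribution. Nor does the SAP say where severe begins, so the line between row (a) and the rest is open.

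The conclusion assumes that Table 2 will be filled as worded and that the case report form adds no separate rash item to the summaries. The primary endpoint is unaffected. The correction is worth making because the review of rash is already required and the comparison between arms is already planned.

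**What to change.** 1. Change the Table 2 skin row to any rash, with severe dermatologic reaction shown as a subset. Fill it from the review in Protocol 5.3 whatever the judged relationship to study drug. The count by arm then no longer depends on an open-label judgement.
2. Reconcile the exceptions so that A4.3, the 7.1 list, the 7.1 closing sentence and the SAP's Safety reporting section state one rule for when an exempt event is reported as an adverse event.

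The cost is one table row and one aligned rule. Active adverse-event review already runs daily through five days (Appendix 1), and Table 2 covers the same period, so no new assessment is needed. The drawback is that, if the case report form captured only severe skin reactions, the records for the treatment days must be queried.

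### The exploratory safety display for patients given both drugs pools azithromycin started before and after randomization and ignores event order, so it can mislead in either direction

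*SAP*

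**What the plan says.** SAP, Concomitant medications, reports that "some patients in the hydroxychloroquine arm received azithromycin either before or in some cases after randomization" and treats these patients as one group. It then plans, as an exploratory summary, that "safety outcomes will be displayed in that group as well as in the groups who received only azithromycin or only hydroxychloroquine".

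Three other statements fix how that display would be filled in:

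- The outcomes are those of SAP Table 2, headed "Table 2 Safety outcomes (measured daily for first five days"). They include death, arrhythmia, cardiac arrest, ARDS and mechanical ventilation.
- The counting rule in SAP, Safety reporting, is that "each patient will be classified as having experienced the outcome at least once (vs. never having experienced the outcome").
- Concomitant drugs, azithromycin among them, "were measured at baseline (before randomization) and through day 5 after randomization".

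Neither document separates the two timings of azithromycin in this display, requires an event to follow azithromycin, or limits the count to conditions that were new after baseline. The protocol defines no such display.

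**The concern.** A patient who already had azithromycin at randomization belongs to the both-drugs group from day 0. A patient who starts it on day 4 joins the group only because of something that happened inside the outcome window, yet the ever/never rule credits that patient's whole five days to both drugs. An arrhythmia on day 1 is then shown under the combination although only one drug had been given. The opposite error also occurs: a patient who dies on day 1 cannot receive azithromycin on day 4 and stays under hydroxychloroquine only. Pooling the two kinds of recipient hides both effects.

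Protocol 5.4.1 raises giving the two drugs together as a QTc concern. The SAP analyses QTc by treatment group. This is the only planned display of the Table 2 outcomes, arrhythmia and cardiac arrest included, for patients who received both drugs. Protocol Appendix 4 generally exempts cardiac arrhythmia and arrest from adverse event reporting unless they are judged related or of uncertain relationship, so a reader interested in the combination is likely to look here.

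**Working it through.** The documents give no figure for this display, so there is nothing to reproduce. The check has three steps.

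**1. The rules side by side.** Exposure window: baseline through day 5. Outcome window: the first five days. Count: ever/never per patient. Grouping: any azithromycin, before or after randomization. The windows overlap and no rule orders event and exposure. Misordering is therefore possible for every after-randomization recipient and for no before-randomization recipient.

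**2. Simple day count, after-randomization recipients only.** Assume that start day and event day are independent and uniform over days 1–5. Of 5 × 5 = 25 equally likely pairs, 10 put the event on a day before azithromycin (10/25 = 40%) and 5 are same-day ties (5/25 = 20%).

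**3. Five-day model in which azithromycin has no effect on the event.** All inputs are assumptions:

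- hydroxychloroquine arm of 150 (half the target of 300; the allocation ratio is not stated);
- five-day event risk R = 0.10 or 0.20, so daily risk h = 1 − (1 − R)^(1/5), which is 0.0209 for R = 0.10;
- prior azithromycin in 0%, 10% or 30% of the arm;
- daily probability of starting azithromycin 0.02 with no event so far, and m × 0.02 once an event has occurred. Within a day the event comes first, so same-day ties count as preceding azithromycin.

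Hand check, m = 1 and no prior use: 150 × (1 − 0.98^5) = 150 × 0.0961 = 14.4 after-randomization recipients.

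One cell in full, R = 0.10, prior use 10%, m = 5: 15 prior recipients at risk 0.10 give 1.5 events, and 15.7 after-randomization recipients at risk 0.256 give 4.02. Risk under both drugs is 5.52/30.7 = 0.180, against 0.080 under hydroxychloroquine only; the ratio is 2.26 before rounding. Of the after-randomization events 87.1% preceded azithromycin, so the share for the whole group is 0.871 × 4.02/5.52 = 63%.

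Risk ratio, both drugs versus hydroxychloroquine only, at R = 0.10 (in brackets, the share of both-drugs events that preceded azithromycin):

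| Prior azithromycin | m = 1 | m = 3 | m = 5 | m = 10 |
|---|---|---|---|---|
| 0% | 1.00 (60%) | 2.12 (81%) | 3.22 (87%) | 6.17 (92%) |
| 10% | 1.00 (28%) | 1.61 (52%) | 2.26 (63%) | 4.16 (75%) |
| 30% | 1.00 (11%) | 1.32 (26%) | 1.68 (36%) | 2.78 (49%) |

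At R = 0.20 the ratios run from 1.00 to 4.62. If the event rules out later azithromycin, as death does, the direction reverses: 0.40, 0.70 and 0.85 for prior use of 0%, 10% and 30% at R = 0.10, and 0.42, 0.72 and 0.86 at R = 0.20.

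Counting events and patient-days by the exposure in force when they occurred gives a rate ratio of 1.00 in every scenario.

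**The case against.** The strongest reply is that this is a descriptive table, labelled exploratory, with no test, threshold or causal statement attached. That stands. A reader might infer that the SAP attributes these events to the combination; it does not, it only displays counts. The main safety summaries, by treatment group among everyone who took study drug, and the QTc comparison do not use this grouping. The exploratory label limits what may be concluded, but it does not put events and exposure in the right order.

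A reader might also infer that worsening is what led to azithromycin. The note in Protocol 5.2.1 covers the case "if the clinical attending physician believes that bacterial pneumonia is likely and requires a second antibacterial agent", but it calls that case uncommon and gives doxycycline and levofloxacin as its examples. The daily medication review in Protocol 5.4.1.2 could discourage azithromycin after a rhythm problem. The documents therefore do not show that m exceeds 1, and for some events it may be below 1.

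Nor should the 40% be read as a distorted comparison. It applies only to after-randomization recipients, whom the SAP describes as some cases, and under the independence that it assumes (m = 1) the ratio is 1.00. What is then wrong is which exposure the events are shown under, not the contrast between groups.

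Finally, before-randomization recipients are not wholly free of timing problems. Patients enter at scale levels 3 to 7, so supplemental oxygen, ventilation or vasopressors may be present at baseline, and the ever/never count does not exclude them.

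The SAP's sensitivity analysis and subgroups on prior azithromycin do not answer the point, because they do not deal with azithromycin started after randomization.

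**Conclusion.** The point holds as a flaw in one exploratory display. Followed as written, the plan shows events that preceded azithromycin under both drugs, and keeps patients whose early event prevented azithromycin under hydroxychloroquine only. The display cannot be relied on even for direction: with no true effect, the assumed scenarios give ratios from 0.40 to 6.17. The ratio departs from 1.00 only if an event changes the chance of starting azithromycin. That is certain for death, and plausible but undocumented for other outcomes. The actual size rests on the number of after-randomization recipients and their timing, neither of which the documents give; the more of the group that had azithromycin before randomization, the smaller the problem. The primary analysis and the randomized safety comparison are not touched. The change is worth making because it is specific and cheap, not because the trial's conclusions are at risk.

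**What to change.** Replace the single both-drugs group with two parts.

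1. **Azithromycin before randomization.** Show hydroxychloroquine-arm patients with any pre-randomization azithromycin, whatever they received later, beside azithromycin-arm patients with pre-randomization azithromycin. Both sides are defined by a baseline fact, so the comparison keeps randomization. Restricting the first group to patients with azithromycin only before randomization would select on a later event and lose that protection.
2. **Azithromycin started after randomization.** Show these patients separately. Count to the combination only new events after the first azithromycin dose; count earlier events and patient-days to hydroxychloroquine alone. State a rule for same-day ties, do not count conditions already present at baseline as new, and label this part non-randomized.

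If azithromycin start dates were not captured, show before and after recipients separately and footnote that events may precede azithromycin.

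The cost is smaller groups and a little more programming. Outcomes are measured daily and medications were recorded through day 5, so the day-level version looks feasible, but the documents do not state that start dates were recorded.
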